Document Date: June 23, 2022

Three Dimensional Assessment of Maxillary Molars Following Distalization Using Two Different Approaches

A Thesis
Submitted to Faculty of Dentistry
Ain-Shams University
In Partial Fulfillment of the Requirements of
Master's Degree in Orthodontics

Faculty of Dentistry
Ain Shams University
2022

Statistical analysis

Statistical analysis was performed with SPSS 20^{®*}, Graph Pad Prism^{®**}, and Microsoft Excel 2016^{***}.

All quantitative data were explored for normality by using Shapiro Wilk Normality test and presented as means and standard deviation (SD) values. All qualitative data were presented as frequency & percentage. All data were presented in (43) tables & (38) graphs.

Tests used:

- Comparisons 2 different groups was performed by using Mann Whitney test.
- Comparisons 2 successive follow ups periods was performed by using Paired t-test.
- Comparison between quantitative continuous data (Age & Duration) was performed by Independent t-test.
- Comparison between qualitative dichotomous data (Gender) was performed by Chi square test.
- Reliability test was performed by using Intra-class Correlation Coefficient (ICC).

* Statistical Package for Social Science, IBM, Armonk, NY, USA.

** Graph Pad Technologies, San Diego, CA, USA

*** Microsoft Co-operation, Redmond, WA, USA.

* All results presented as:

I. Normality test.

II. Baseline characteristics:

- A. Age.
- B. Gender.
- C. Duration
- D. Pretreatment measurements. (Appendix IV).

III. Measurements

The following measurements were carried for both group I and group II as well as in comparison between the two groups.

A. Skeletal measurements

- 1. Skeletal antero-posterior measurements.
- 2. Skeletal vertical measurements.

B. Dental measurements

- 1. Angular
- 2. Linear

C. Soft tissue measurements.

IV. Reliability: (Appendix V)

- A. Inter-observer.
- B. Intra-observer.

I. Normality test:

Exploration of the given data was performed using Shapiro-Wilk test and Kolmogorov-Smirnov test for normality. As Listed in (Table 11) and showed in (Figure 53), it was revealed that the significant level (P-value) was shown to be insignificant as P-value > 0.05 , which indicated that alternative hypothesis was rejected, and the concluded data originated from normal distribution (parametric data) resembling normal Bell curve in pre & post measurements while P value was significant in the difference between both groups which indicated nonparametric data.

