Table (11): Normality exploration of both groups regarding all measurements:

Measurements		Group I Single Coil Spring	Group II Double Coil Spring
Skeletal.	Pre	> 0.05	> 0.05
	Post	> 0.05	> 0.05
	Difference	$< 0.05^*$	$< 0.05^*$
Dental	Pre	> 0.05	> 0.05
	Post	> 0.05	> 0.05
	Difference	$< 0.05^*$	$< 0.05^*$
Soft tissue	Pre	> 0.05	> 0.05
	Post	> 0.05	> 0.05
	Difference	$< 0.05^*$	$< 0.05^*$

* Significant difference as $P < 0.05$

[figure not shown]
[figure not shown]

Figure (53): Scattered chart represents normal bell curve of normality test.

II. Baseline characterized:

1. Age:

In group I, minimum age was (18.4), maximum was (21.2), while mean \pm standard deviation was (19.42 ± 1.03) . In group II, minimum age was (18.08), maximum was (23.17), while mean \pm standard deviation was (20.7 ± 2.24) , as presented in table (12) and figure (54).

Comparison between both groups was performed by using Independent t-test which revealed insignificant difference between them as $P > 0.05$, as presented in table (12).

Table (12): Minimum, maximum, mean & standard deviation of age in both groups:

	Min	Max	M	SD	P value
G I	18.4	21.2	19.42	1.03	0.09
G II	18.08	23.17	20.7	2.24	

N: count

Min: minimum

Max: maximum

M: mean

SD: standard deviation

[figure not shown]

Figure (54): Bar chart showing mean of age in both groups.

2. Gender:

In gender all companions were performed by using Chi square test. In group I, male (16.67%) was significantly lower than female (83.3%) as $P < 0.05$, while in group II male (33.3%) was insignificantly lower than female (66.6%) as $P > 0.05$, as presented in table (13) and figure (55).

Also, comparison between group I & II reveled insignificant difference between them in both male & female as $P > 0.05$ as presented in table (13).

Table (13): Frequency & percentage of gender distribution in both groups:

Group	Male		Female		P value
	N	%	N	%	
Group I	2	16.67%	10	83.33%	0.001*
Group II	3	33.33%	6	66.67%	0.13
P value	0.34		0.34		

N: count

%: percentage

P: probability level which is significant at $P \leq 0.05$

[figure not shown]

Figure (55): Bar chart showing percentage of gender distribution in both groups

3. Duration:

In group I, minimum duration was (5.5 months), maximum was (9.73 months), while mean \pm standard deviation was (8.03 ± 2.9) . In group II, minimum duration was (4 months), maximum was (14.9 months), while mean \pm standard deviation was (10.59 ± 3.89) .

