U4-apex/S Ver	57.08	3.56	59.67	3.11	2.59	1.64	0.010*
U5-tip/S Ver	54.68	3.61	56.08	3.71	1.40	1.00	0.000**
U5-apex/S Ver	52.57	2.51	54.42	2.71	1.86	1.55	0.001*
MBc6/S Ver	48.60	3.53	44.82	3.35	-3.78	1.31	0.002*
U6-apex/S Ver	47.70	3.06	44.92	2.83	-2.78	1.64	0.000**
MBc7/S Ver	37.47	3.57	34.21	3.32	-3.26	1.55	0.000**
U7-apex/S Ver	37.79	2.65	35.29	3.44	-2.50	2.45	0.000**
overjet	6.30	3.52	7.48	5.46	1.19	2.43	0.311

M: mean

SD: standard deviation

MD: mean difference

P: probability level which is significant at $P \leq 0.05$

[figure not shown]

Figure (72): Bar chart showing mean of pretreatment, post treatment records and difference between them regarding anteroposterior - linear dental measurements in group I.

- **Group II:**

In group II pretreatment records, post treatment records and difference between them regarding anteroposterior- linear- dental measurements were presented in table (31) and figure (73).

Comparison between pretreatment & post treatment records was performed by using Paired t-test which revealed insignificant difference between them in all measurements as $P > 0.05$ except U4-apex/S Ver U5-tip/S Ver, U5-apex/S Ver (Post was significantly higher than prerecord and MBc6/S Ver , U6-apex/S Ver , MBc7/S Ver & U7-apex/S Ver (Post was significantly lower than prerecord), as there was a statistical significant difference as $P < 0.05$, , as presented in table (31).

Table (31): Mean & standard deviation of pretreatment, post treatment records and difference between them regarding anteroposterior - linear dental measurements in group II:

Group II Anteroposterior Linear Dental Measurements	pre		post		Difference		P value
	M	SD	M	SD	MD	SD	
U1-tip/S Ver	76.89	2.86	77.48	2.99	0.59	0.13	0.12
U1-apex/ S Ver	67.13	3.09	67.56	3.18	0.43	0.08	0.25
L1-tip/S Ver	72.48	3.32	71.93	4.20	-0.54	1.61	0.342
U4-tip/S Ver	63.21	3.81	64.32	4.43	1.11	1.76	0.095
U4-apex/S Ver	57.90	3.53	59.69	2.68	1.79	1.19	0.002*
U5-tip/S Ver	56.43	3.58	58.31	3.87	1.88	1.49	0.005*
U5-apex/S Ver	53.48	2.83	54.85	2.27	1.37	1.58	0.031*
MBc6/S Ver	50.55	3.53	46.04	5.61	-4.51	3.39	0.004*
U6-apex/S Ver	48.06	3.97	45.94	5.17	-2.12	2.52	0.035*
MBc7/S Ver	39.93	3.98	34.61	5.39	-5.32	3.62	0.002*
U7-apex/S Ver	39.18	3.01	36.79	2.75	-2.40	0.98	0.000**
overjet	4.46	1.63	5.31	1.99	0.85	1.25	0.074

M: mean

SD: standard deviation

MD: mean difference

P: probability level which is significant at $P \leq 0.05$

[figure not shown]

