Figure (73): Bar chart showing mean of pretreatment, post treatment records and difference between them regarding anteroposterior linear dental measurements in group II.

- **Comparison between both groups:**

Comparison between group I & II regarding difference between pretreatment & posttreatment records of anteroposterior - linear dental measurements was performed by using Mann Whitney test which revealed insignificant difference between them regarding all measurements except U1-tip/S Ver (Group I was significantly lower than group II) as $P <0.05$, as presented in table (32) and figure (74).

Table (32): Comparison between both groups regarding anteroposterior - linear dental measurements:

[figure not shown]
Difference Anteroposterior Linear Dental Measurements	Group I		Group II		P value
	MD	SD	MD	SD	
U1-tip/S Ver	0.02	0.47	0.59	0.13	0.002*
U1-apex/ S Ver	-0.02	1.21	0.43	0.08	0.28
L1-tip/S Ver	-1.16	2.50	-0.54	1.61	1
U4-tip/S Ver	1.06	1.17	1.11	1.76	0.97
U4-apex/S Ver	2.59	1.64	1.79	1.19	0.31
U5-tip/S Ver	1.40	1.00	1.88	1.49	0.71
U5-apex/S Ver	1.86	1.55	1.37	1.58	0.71
MBc6/S Ver	-3.78	1.31	-4.51	3.39	0.8
U6-apex/S Ver	-2.78	1.64	-2.12	2.52	1
MBc7/S Ver	-3.26	1.55	-5.32	3.62	0.12
U7-apex/S Ver	-2.50	2.45	-2.40	0.98	0.86
overjet	1.19	2.43	0.85	1.25	0.75

SD: standard deviation

MD: mean difference

P: probability level which is significant at $P \leq 0.05$

Figure (74): Bar chart showing comparison between both groups regarding anteroposterior linear dental measurements.

b. Vertical

- Group I:**

In group I pretreatment records, post treatment records and difference between them regarding vertical- linear- dental measurements were presented in table (33) and figure (75).

Comparison between pretreatment & post treatment records was performed by using Paired t-test which revealed significant difference between them in all measurements as $P < 0.05$ except overbite as there was insignificant difference between pre & post as $P > 0.05$. In U1-tip/PP, pre was significantly lower than post, while in U4-tip/PP, U5-tip/PP, MBc6/PP, MBc7/PP and L1-tip/PP pre was significantly higher than post as $P < 0.05$, as presented in table (33).

Table (33): Mean & standard deviation of pretreatment, post treatment records and difference between them regarding vertical - linear dental measurements in group I:

Group I Vertical Linear Dental Measurements	Pre		Post		Difference		P value
	M	SD	M	SD	MD	SD	
U1-tip/PP	27.68	3.67	27.86	3.67	0.18	0.52	0.005*

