U4-tip/PP	25.79	3.18	25.10	3.00	-0.69	0.56	0.001*
U5-tip/PP	25.25	2.82	24.56	3.01	-0.70	0.63	0.001*
MBc6/PP	23.90	2.50	22.75	2.75	-1.15	0.88	0.003*
MBc7/PP	21.43	2.81	20.77	3.24	-0.65	0.91	0.001*
L1-tip/PP	24.45	3.73	23.63	5.55	-0.82	2.67	0.008*
overbite	3.23	1.14	4.23	2.57	1.00	2.68	0.119

M: mean

SD: standard deviation

MD: mean difference

P: probability level which is significant at $P \leq 0.05$

[figure not shown]

Figure (75): Bar chart showing mean of pretreatment, post treatment records and difference between them regarding vertical linear dental measurements in group I.

- **Group II:**

In group II pretreatment records, post treatment records and difference between them regarding vertical- linear- dental measurements were presented in table (34) and figure (76).

Comparison between pretreatment & post treatment records was performed by using Paired t-test which revealed insignificant difference between them in all measurements as $P > 0.05$ except U4-tip/PP, MBc6/PP & MBc7/PP as Pre was significantly higher than post as $P < 0.05$., as presented in table (34).

Table (34): Mean & standard deviation of pretreatment, post treatment records and difference between them regarding vertical - linear dental measurements in group II:

Group II Vertical Linear Dental Measurements	pre		post		Difference		P value
	M	SD	M	SD	M	SD	
U1-tip/PP	27.78	3.27	28.05	3.19	0.27	-0.09	0.16
U4-tip/PP	25.98	2.93	25.25	3.13	-0.73	0.86	0.036*
U5-tip/PP	25.21	3.05	24.76	3.62	-0.45	1.36	0.352
MBc6/PP	24.00	3.28	22.47	3.13	-1.53	1.21	0.005*
MBc7/PP	22.00	3.65	20.11	3.72	-1.88	1.83	0.015*
L1-tip/PP	24.74	4.08	24.18	4.37	-0.56	1.79	0.374
overbite	3.56	2.61	4.67	2.43	1.11	1.47	0.053

M: mean

SD: standard deviation

MD: mean difference

P: probability level which is significant at $P \leq 0.05$

[figure not shown]

Figure (76): Bar chart showing mean of pretreatment, post treatment records and difference between them regarding vertical linear dental measurements in group II.

- **Comparison between both groups:**

Comparison between group I & II regarding difference between pretreatment & posttreatment records of vertical - linear dental measurements was performed by using Mann Whitney test which revealed insignificant difference between them regarding all measurements, as presented in table (35) and figure (77).

Table (35): Comparison between both groups regarding vertical - linear dental measurements:

Difference Vertical Linear Dental Measurements	Group I		Group II		P value

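### Overjet and overbite equal upper minus lower incisor tip in every Group I mean but in no Group II mean, so the Group II incisor, overjet and overbite rows do not reconcile; which conclusion is affected depends on the source

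*SAP*

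**What the plan says.** SAP section III.B.2 (linear dental measurements) reports U1-tip, L1-tip and overjet against the vertical reference line S Ver in Table 30 (Group I) and Table 31 (Group II). It reports U1-tip, L1-tip and overbite against the palatal plane (PP) in Tables 33 and 34.

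For Group II, Table 31 has "overjet 4.46 1.63 5.31 1.99 0.85 1.25 0.074" and Table 34 has "overbite 3.56 2.61 4.67 2.43 1.11 1.47 0.053". The columns are pre mean and SD, post mean and SD, change and its SD, and paired P.

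Table 32 compares the changes between groups. Its text finds nothing significant "except U1-tip/S Ver (Group I was significantly lower than group II"), with P 0.002.

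The tests are listed as "Comparisons 2 successive follow ups periods was performed by using Paired t-test" and "Comparisons 2 different groups was performed by using Mann Whitney test". Group sizes come from Table 13: "Group I 2 16.67% 10 83.33% 0.001" and "Group II 3 33.33% 6 66.67% 0.13", that is 12 and 9 patients. Neither document defines overjet or overbite, gives an n for each measurement, or mentions missing or excluded measurements.

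**The concern.** Within one set of patients, the mean of a difference equals the difference of the means, whatever the SDs. If overjet is U1-tip minus L1-tip along the same axis, the three means must agree to rounding, and likewise for overbite. Group I behaves this way throughout and Group II does not.

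Two things are at stake. First, if overjet or overbite was obtained differently in the two arms, or from different patients, the between-group comparison is not like with like. Second, the Group II U1-tip row feeds the only significant between-group result in Table 32. The Protocol's introduction, describing earlier work, attributes increased overjet to anchorage loss, so a reader will take these rows as evidence on how well the anterior teeth held.

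**Working it through.** **Inputs.** Means, change SDs and P values from Tables 30 to 34; n = 12 and n = 9 from Table 13; two-sided tests assumed. Only the means and change SDs are used from Group I.

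**Step 1: reproduce the printed Group II P values.** Paired t = change / (SD/√9), 8 df.
- Overjet: 0.85/(1.25/3) = 2.04, P = 0.076 (printed 0.074; rounding of the inputs allows 0.073 to 0.078).
- Overbite: P = 0.053 (printed 0.053).
- L1-tip/S Ver: P = 0.344 (printed 0.342).
- L1-tip/PP: P = 0.375 (printed 0.374).
- U1-tip/S Ver: 0.59/(0.13/3) = 13.6, P < 0.0001 (printed 0.12). The printed P implies a change SD of about 1.02.

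**Step 2: the identity.** U1-tip minus L1-tip, against the printed mean:

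| | U1 − L1 | Printed | Gap |
|---|---|---|---|
| I overjet pre | 78.77 − 72.47 = 6.30 | 6.30 | 0.00 |
| I overjet post | 78.79 − 71.31 = 7.48 | 7.48 | 0.00 |
| I overbite pre | 27.68 − 24.45 = 3.23 | 3.23 | 0.00 |
| I overbite post | 27.86 − 23.63 = 4.23 | 4.23 | 0.00 |
| II overjet pre | 76.89 − 72.48 = 4.41 | 4.46 | −0.05 |
| II overjet post | 77.48 − 71.93 = 5.55 | 5.31 | +0.24 |
| II overbite pre | 27.78 − 24.74 = 3.04 | 3.56 | −0.52 |
| II overbite post | 28.05 − 24.18 = 3.87 | 4.67 | −0.80 |

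Three means, each rounded to within 0.005, can disagree by at most 0.015 mm. Group II changes also conflict: overjet 0.59 − (−0.54) = 1.13 against 0.85, and overbite 0.27 − (−0.56) = 0.83 against 1.11.

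**Step 3: what follows from each possible source.**

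*Overjet, overbite and L1-tip right; U1-tip wrong.* The U1-tip/S Ver change is 0.85 − 0.54 = 0.31 mm, so the between-group difference falls from 0.59 − 0.02 = 0.57 to 0.31 − 0.02 = 0.29 mm. Welch test, SE = √(0.47²/12 + SD²/9):

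| Group II SD | Difference 0.57 | Difference 0.29 |
|---|---|---|
| 0.13 (printed) | P 0.0015 | P 0.06 |
| 0.5 (assumed) | P 0.017 | P 0.20 |
| 1.02 (implied by P 0.12) | P 0.15 | P 0.45 |

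Vertically, the U1-tip/PP change becomes (4.67 + 24.18) − (3.56 + 24.74) = 0.55 rather than 0.27. At the SD of 0.52 that the printed P of 0.16 implies, paired P would be 0.013.

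*Incisor rows right; overjet and overbite wrong.* The overjet change is 1.13 mm. It reaches P ≤ 0.05 only if its SD is at most 1.13 × 3/2.306 = 1.47. At the printed 1.25, t = 2.71 and P = 0.027. The printed incisor SDs (0.13 and 1.61), however, force an SD between 1.61 − 0.13 = 1.48 and 1.61 + 0.13 = 1.74, giving P 0.051 to 0.087. With a U1-tip SD of 1.02, significance needs a correlation between U1 and L1 changes of about 0.45 or more. Between groups, 1.19 against 1.13 gives P of about 0.94. The overbite change becomes 0.83, P 0.13 at the printed SD, still not significant.

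*L1-tip wrong.* The changes become (77.48 − 5.31) − (76.89 − 4.46) = −0.26 (P 0.64) and (28.05 − 4.67) − (27.78 − 3.56) = −0.84 (P 0.20) at the printed SDs. Neither is significant, as printed.

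**The case against.** The mismatch itself is hard to dispute: pre, post and change agree within each Group II row to 0.01 mm, so there is no sign of a text-extraction fault. The objections concern what may be built on it, and most of them stand.

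- **Are the means wrong?** A reader might infer so. But no definition and no n per row is given. If overjet was measured directly in one arm, or on a different set of patients, every printed mean could be correct.
- **Are the U1 rows the culprit?** It is tempting to say so because overjet, overbite and L1-tip reproduce their paired P values and U1-tip does not. That check tests only whether change, SD and n agree within a row. U1-tip fails on its SD column, which looks like post SD minus pre SD (2.99 − 2.86 = 0.13; for U1-tip/PP, 3.19 − 3.27 = −0.08 against a printed −0.09, impossible for an SD). It says little about the U1 means.
- **Does any correction change a conclusion?** No. The overjet reversal at P 0.027 borrows its SD from the very row that this reading treats as wrong. Correcting L1-tip, or overbite alone, changes nothing.
- **Does the mean error alone sink the U1-tip result?** Not clearly. An SD of 1.02 already gives P of about 0.15 at the printed mean. At the printed SD, the corrected mean gives a borderline 0.06. Table 32 used Mann-Whitney, which cannot be rerun from summaries. In simulated normal samples matched to a change of 0.31 and SD 0.13, the median Mann-Whitney P was 0.10 and about 25% of samples still fell at or below 0.05.
- **Importance.** Neither document ranks these rows as a primary measure. The Protocol's methods of assessment are rate of tooth movement and CBCT, and the thesis title concerns the molars.

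**Conclusion.** The inconsistency is established from printed means alone: four of four Group I means satisfy the relation and none of four in Group II does, with gaps of 0.05 to 0.80 mm against about 0.015 mm for rounding. The Group II U1-tip, L1-tip, overjet and overbite rows cannot all describe the same nine patients under the relation that holds in Group I. Either some means are wrong, or the definition or patient set differs between arms. The documents do not settle which.

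The consequence is conditional on that source. The result most exposed is the U1-tip/S Ver difference in Table 32. It is in doubt on two separate grounds: its mean, if overjet and L1-tip are right, and its SD of 0.13, which contradicts the same row's paired P of 0.12 whichever mean is right. A significant Group II overjet increase is possible but not shown. The P values for alternative scenarios are t-test approximations at stated or assumed SDs.

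**What to change.** From the same nine patients' landmarks, recompute the Group II rows for U1-tip/S Ver, L1-tip/S Ver, U1-tip/PP, L1-tip/PP, overjet and overbite: means, change SDs and P values. State one definition of overjet and overbite and apply it in both arms. If they were measured directly rather than derived, say so; the relation then need not hold patient by patient. Give the n for each row.

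Correct Tables 31, 32, 34 and 35 and their text. Hold the statement that Group I was significantly lower than Group II for U1-tip/S Ver until the rows reconcile and the Mann-Whitney test has been rerun.

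The cost is reanalysis of existing data, with no new measurements if the landmark data are held. The single significant result in Table 32 may be lost.

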Comparison between pretreatment & post treatment records was performed by using Paired t-test which revealed insignificant difference between them in all measurements as $P > 0.05$ except U1-FHP and U5-FHP (Post was significantly higher than prerecord) as $P < 0.05$, as presented in table (21).

Table (21): Mean & standard deviation of pretreatment, post treatment records and difference between them regarding anteroposterior angular dental measurements in group I:

Group I Anteroposterior Angular Dental Measurements	Pre		Post		Difference		P value
	M	SD	M	SD	MD	SD	
U1-NA	25.83	9.57	26.27	10.17	0.44	1.88	0.437
U1-FHP	123.54	12.59	124.50	12.88	0.97	1.46	0.042*
U4-FHP	102.14	9.64	103.24	11.70	1.10	4.80	0.444
U5-FHP	96.83	11.01	101.88	13.25	5.06	6.02	0.014*
U6-FHP	94.43	8.90	89.70	9.02	-4.72	9.69	0.119
U7-FHP	87.70	10.16	82.83	8.09	-4.87	8.16	0.063

M: mean

SD: standard deviation

MD: mean difference

P: probability level which is significant at $P \leq 0.05$

[figure not shown]

Figure (63): Bar chart showing mean of pretreatment, post treatment records and difference between them regarding anteroposterior angular dental measurements in group I.

- **Group II:**

In group II pretreatment records, post treatment records and difference between them regarding anteroposterior- angular- dental measurements were presented in table (22) and figure (64).

Comparison between pretreatment & post treatment records was performed by using Paired t-test which revealed insignificant difference between them in all measurements as $P > 0.05$ except U4-FHP and U5-FHP (Post records were significantly higher than prerecords), and U6-FHP (Post record was significantly lower than prerecord) as $P < 0.05$, as presented in table (22).

Table (22): Mean & standard deviation of pretreatment, post treatment records and difference between them regarding anteroposterior angular dental measurements in group II:

Group II Anteroposterior Angular Dental Measurements	pre		post		Difference		P value
	M	SD	M	SD	MD	SD	
U1-NA	16.88	4.94	17.05	5.79	0.18	0.85	0.67
U1-FHP	114.61	4.00	115.05	4.83	0.43	0.83	0.44
U4-FHP	105.26	5.30	109.68	4.81	4.42	5.18	0.034*
U5-FHP	102.27	4.80	108.52	5.79	6.25	5.34	0.008*
U6-FHP	97.77	1.80	84.23	9.21	-13.54	8.61	0.002*
U7-FHP	88.47	8.81	80.17	9.62	-8.30	0.81	0.077

M: mean

SD: standard deviation

MD: mean difference

P: probability level which is significant at $P \leq 0.05$

[figure not shown]

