Figure (66): Bar chart showing pretreatment, post treatment records and difference between them regarding rotation angular dental measurements in group I.

- **Group II:**

In group II pretreatment records, post treatment records and difference between them regarding rotation- angular- dental measurements were presented in table (25) and figure (67).

Comparison between pretreatment & post treatment records was performed by using Paired t-test which revealed insignificant difference between them in all measurements as $P > 0.05$ except U5-MSP and U6-MSP as there was a statistical significant difference as $P < 0.05$ (Post was significantly higher than prerecord), as presented in table (25).

Table (25): Mean & standard deviation of pretreatment, post treatment records and difference between them regarding rotation angular dental measurements in group II:

Group II Rotation Angular Dental Measurements	pre		post		Difference		P value
	M	SD	M	SD	MD	SD	
U4-MSP	74.75	5.74	75.51	7.01	0.76	7.22	0.761
U5-MSP	76.26	10.52	56.45	9.88	-19.81	11.69	0.001*
U6-MSP	32.33	6.82	51.46	19.53	19.13	19.26	0.018*
U7-MSP	37.63	6.55	64.09	13.42	26.47	6.87	0.057

M: mean

SD: standard deviation

MD: mean difference

P: probability level which is significant at $P \leq 0.05$

[figure not shown]

Figure (67): Bar chart showing mean of pretreatment, post treatment records and difference between them regarding rotation angular dental measurements in group II.

- **Comparison between both groups:**

Comparison between group I & II regarding difference between pretreatment & posttreatment records of rotation - angular dental measurements was performed by using Mann Whitney test which revealed insignificant difference between them regarding all measurements except U5-MSP (Group I was significantly higher than group II) as $P < 0.05$, as presented in table (26) and figure (68).

Table (26): Comparison between both groups regarding rotation angular dental measurements:

Difference Rotation Angular Dental Measurements	Group I		Group II		P value
	MD	SD	MD	SD	
U4-MSP	3.06	8.70	0.76	7.22	0.75
U5-MSP	-5.48	4.79	-19.81	11.69	0.009*
U6-MSP	18.12	8.35	19.13	19.26	0.45
U7-MSP	10.84	8.06	26.47	6.87	0.06

SD: standard deviation

MD: mean difference

P: probability level which is significant at $P \leq 0.05$

[figure not shown]

Figure (68): Bar chart showing comparison between both groups regarding rotation angular dental measurements.

c. Crown inclination

- **Group I:**

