	MD	SD	MD	SD	
U1-tip/PP	0.18	0.52	0.27	-0.09	0.61
U4-tip/PP	-0.69	0.56	-0.73	0.86	0.81
U5-tip/PP	-0.70	0.63	-0.45	1.36	0.86
MBc6/PP	-1.15	0.88	-1.53	1.21	0.81
MBc7/PP	-0.65	0.91	-1.88	1.83	0.11
L1-tip/PP	-0.82	2.67	-0.56	1.79	0.65
overbite	1.00	2.68	1.11	1.47	0.27

SD: standard deviation

MD: mean difference

P: probability level which is significant at $P \leq 0.05$

[figure not shown]

Figure (77): Bar chart showing comparison between both groups regarding vertical linear dental measurements

c. Transverse

- **Group I:**

In group I pretreatment records, post treatment records and difference between them regarding transverse- linear- dental measurements were presented in table (36) and figure (78).

Comparison between pretreatment & post treatment records was performed by using Paired t-test which revealed significant difference between them in all measurements as $P < 0.05$ except U4 as there was insignificant difference between pre & post as $P > 0.05$. In U5, there was a statistically significant difference as $P < 0.05$ (pre was significantly lower than post), while in U6 and U7 there was a highly statistical significant difference as $P < 0.001$ (pre was significantly lower than post), as presented in table (36).

Table (36): Mean & standard deviation of pretreatment, post treatment records and difference between them regarding transverse - linear dental measurements in group I:

Group I Transverse Linear Dental Measurements	Pre		Post		Difference		P value
	M	SD	M	SD	MD	SD	
U4	16.80	2.01	18.55	2.03	1.75	1.36	0.438
U5	18.83	2.06	20.84	1.94	2.01	1.11	0.001*
U6	21.96	2.21	23.39	2.06	1.43	0.98	0.000**
U7	24.50	2.55	25.45	2.50	0.95	1.01	0.000**

M: mean

SD: standard deviation

MD: mean difference

P: probability level which is significant at $P \leq 0.05$

[figure not shown]

Figure (78): Bar chart showing mean of pretreatment, post treatment records and difference between them regarding transverse - linear dental measurements in group I.

- **Group II:**

In group II pretreatment records, post treatment records and difference between them regarding transverse- linear- dental measurements were presented in table (37) and figure (79).

Comparison between pretreatment & post treatment records was performed by using Paired t-test which revealed insignificant difference between them in all measurements as $P < 0.05$, as presented in table (37).

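### Eight Group II SDs of change are post SD minus pre SD (one is negative), and the Group I paired P values in Tables 30, 33 and 36 do not fit their rows; four significance labels reverse and the one significant result in Table 32 is unverified

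*SAP*

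**What the plan says.** Under Tests used, the SAP assigns a paired t-test to pre/post comparisons and a Mann-Whitney test to comparisons between groups. Section I (Normality test) calls the pre and post values normal and the changes nonparametric. Table 13 gives 12 patients in Group I and 9 in Group II.

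For Group II, Table 31 prints "U1-tip/S Ver 76.89 2.86 77.48 2.99 0.59 0.13 0.12" (pre mean and SD, post mean and SD, mean change, SD of change, paired P). Table 32 carries the change into the between-group comparison as "U1-tip/S Ver 0.02 0.47 0.59 0.13 0.002", and the text says the test showed "insignificant difference between them regarding all measurements except U1-tip/S Ver (Group I was significantly lower than group II").

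Other Group II rows of the same kind are "U7-FHP 88.47 8.81 80.17 9.62 -8.30 0.81 0.077" (Table 22), "U7-MSP 37.63 6.55 64.09 13.42 26.47 6.87 0.057" (Table 25) and "U1-tip/PP 27.78 3.27 28.05 3.19 0.27 -0.09 0.16" (Table 34). The last is repeated between groups in Table 35 as "U1-tip/PP 0.18 0.52 0.27 -0.09 0.61". The Table 25 text reports "insignificant difference between them in all measurements as $P > 0.05$ except U5-MSP and U6-MSP", so U7-MSP is described as unchanged.

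In Group I, Table 30 prints 78.77 as the P value for U1-tip/S Ver. The text accompanying Tables 30, 33 and 36 repeats the significance labels of the printed P columns.

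**The concern.** An SD cannot be negative. A P value cannot exceed 1. A mean change of 0.59 with SD 0.13 in nine patients cannot give a paired P of 0.12. Errors of this kind suggest that SDs were obtained by subtracting one column from another and that some P values sit against the wrong row.

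Three things are at stake. U1-tip/S Ver is the only between-group difference called significant in Table 32, and a reader cannot tell whether its P is a rank-test result or a t-test on a wrong SD. Several within-group statements in the text may say the opposite of what the data show. The faulty SDs also pass into Tables 20, 23, 26, 32 and 35, where anyone pooling or re-using the results would take them as they stand.

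**Working it through.** **Inputs.** Printed means, SDs and P values from the SAP tables; n = 12 (2 + 10) and n = 9 (3 + 6) from Table 13. Printed values may be off by ±0.005 through rounding. Tests are taken as two-sided.

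**Formulas.** Paired t = mean change ÷ (SD of change ÷ √n), with n − 1 degrees of freedom. The SD of change satisfies SD² = s₀² + s₁² − 2r·s₀·s₁, where s₀ and s₁ are the pre and post SDs and r is their correlation. So it lies between |s₁ − s₀| (only if r = 1) and s₀ + s₁ (only if r = −1).

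**Control.** Of the 48 Group II rows, 40 reproduce their printed paired P. The test and n = 9 are therefore right, and the other eight rows are the exceptions.

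**The eight Group II rows (n = 9)**

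| Row (table) | s₁ − s₀ | Printed SD | P from printed SD | Printed P |
|---|---|---|---|---|
| PP-SN (19) | 3.31 − 3.58 = −0.27 | 0.27 | 0.096 | 0.54 |
| U1-NA (22) | 5.79 − 4.94 = 0.85 | 0.85 | 0.54 | 0.67 |
| U1-FHP (22) | 4.83 − 4.00 = 0.83 | 0.83 | 0.16 | 0.44 |
| U7-FHP (22) | 9.62 − 8.81 = 0.81 | 0.81 | 1e-09 | 0.077 |
| U7-MSP (25) | 13.42 − 6.55 = 6.87 | 6.87 | 3e-06 | 0.057 |
| U1-tip/S Ver (31) | 2.99 − 2.86 = 0.13 | 0.13 | 8e-07 | 0.12 |
| U1-apex/S Ver (31) | 3.18 − 3.09 = 0.09 | 0.08 | 2e-07 | 0.25 |
| U1-tip/PP (34) | 3.19 − 3.27 = −0.08 | −0.09 | 2e-05 (using 0.09) | 0.16 |

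For U1-tip/S Ver: t = 0.59 ÷ (0.13 ÷ 3) = 13.6 on 8 df. In the first three rows the conclusion is the same either way. In the last five the printed SD and the printed P fall on opposite sides of 0.05.

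**U7-MSP, Group II.** The largest possible SD of change is 6.55 + 13.42 = 19.97. Then t = 26.47 ÷ (19.97 ÷ 3) = 3.98 and P = 0.0041. A P of 0.057 would need four or fewer patients: the bound is 0.077 at n = 4 and 0.041 at n = 5.

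**The 0.002 in Table 32.** A pooled t-test of 0.02 (SD 0.47, n = 12) against 0.59 (SD 0.13, n = 9) gives P = 0.0023. Across the eight rows, the P labelled Mann-Whitney matches a pooled t on the faulty SD, within rounding, in six: 0.662/0.66, 0.705/0.70, 0.334/0.33, 0.0023/0.002, 0.282/0.28 and 0.616/0.61. It does not match for U7-FHP (0.227/0.16) or U7-MSP (0.0002/0.06). Only 3 of the other 40 rows match. Against this, the exact Mann-Whitney P at 12 v 9 without ties is 0.0018 for U = 12 and 0.0024 for U = 13, so 0.002 is also attainable by the stated test.

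*Sensitivity only.* If the paired P of 0.12 were right, the Group II SD would be 0.59 × 3 ÷ 1.74 ≈ 1.02, and the between-group t-test would give about 0.10 (Welch 0.15).

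**Group I paired P values (n = 12).** In Tables 30, 33 and 36, 16 to 18 of 23 disagree with the printed mean and SD, depending on tolerance. In the other Group I tables 3 of 25 do. Four labels reverse:

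| Row (table) | Mean change, SD | P recomputed | Printed P |
|---|---|---|---|
| U4-tip/S Ver (30) | 1.06, 1.17 | 0.009 | 0.124 |
| U1-tip/PP (33) | 0.18, 0.52 | 0.26 | 0.005* |
| L1-tip/PP (33) | −0.82, 2.67 | 0.31 | 0.008* |
| U4 transverse (36) | 1.75, 1.36 | 0.001 | 0.438 |

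Three printed values lie outside what any SD of change allows:
- L1-tip/S Ver: SD at most 3.99 + 4.58 = 8.57, so P ≤ 0.65; 0.948 is printed.
- L1-tip/PP: SD at least 5.55 − 3.73 = 1.82 (1.81 allowing for rounding), so P ≥ 0.14; 0.008 is printed.
- U4 transverse: SD at most 2.01 + 2.03 = 4.04, so P ≤ 0.16; 0.438 is printed and would need an SD of about 7.5.

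**Signs of displacement.** In Table 30 the P printed one row lower fits in 9 of 11 rows, against 3 of 12 in place. L1-tip/PP recomputes to 0.310, and 0.311 is printed at overjet. Overjet recomputes to 0.118, and 0.119 is printed at overbite. In Table 18, PP-SN and MP-SN recompute to 0.263 and 0.41 against printed 0.425 and 0.265. They look swapped, with no change of label.

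**The case against.** The strongest objection concerns the 0.002. Mann-Whitney works on ranks and never uses the SD, so a wrong SD in Table 31 does not by itself disturb the P in Table 32. Every Mann-Whitney P in the document is equally uncheckable without patient data, and the pooled-t match fails for the two U7 rows. This stands, and it is why the result is called unverified. Those two rows also print their paired P to three decimals like the rest of Group II, whereas the six matching rows print two. That split fits a separate source for the six, but does not prove one.

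The implied SD of 1.02 relies on a paired P not known to be sound and on a t-test for changes the SAP calls non-normal. It does not show that significance is lost. For seven of the eight rows a larger, feasible SD would reconcile the printed P, so only the U7-MSP P is shown to be impossible.

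The displacement account for Group I is also conjecture. Many of the fitting values are 0.000 or 0.001 and discriminate little, and many mismatches stay below 0.05 either way. The mismatch itself does not depend on that account. PDF extraction does not explain the reversed labels, because the text repeats them.

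Finally, neither document names U1-tip/S Ver as a primary outcome, and most of the effect is on within-group labels.

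**Conclusion.** The concern holds. Eight Group II SDs of change are wrong: they equal post SD minus pre SD in size (six exactly, two within 0.01), and all eight fail a check that the other 40 rows pass. The Group II U7-MSP paired P of 0.057 is impossible given its own means and SDs at n = 9. In Group I, one P exceeds 1, three more are infeasible, and four labels reverse on the printed mean and SD; those four reverse at every n tried from 8 to 24. The 0.002 for U1-tip/S Ver is neither confirmed nor refuted.

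This rests on the printed pre and post means and SDs being right and on the Table 13 counts, which the control rows support.

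The reach is limited. The other significant between-group results (U6-FHP, U5-MSP, U6 inclination, U5 transverse) do not use the eight SDs, and no between-group P is derived from the Group I paired P column. Correction is still required, because the text as it stands states results that its own tables contradict.

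**What to change.** Work from each patient's post minus pre change.

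1. For the eight Group II rows, recompute the SD of change and the paired P, and replace whatever differs. Carry the SDs into Tables 20, 23, 26, 32 and 35, and rerun the Mann-Whitney test for those rows. Keep the U1-tip/S Ver claim only if it reproduces.
2. Change the wording on Group II U7-MSP if recomputation confirms the bound, as the printed SDs and n = 9 imply it will.
3. Recompute all 23 Group I paired P values in Tables 30, 33 and 36, and PP-SN and MP-SN in Table 18. Correcting 78.77 alone, or shifting the column by one row, is not enough: for L1-tip/S Ver (0.136), U1-tip/PP (0.256), MBc7/PP (0.031) and overbite (0.223), no P printed in those three tables fits.
4. Correct the text for every label that changes, including U4-tip/S Ver, U1-tip/PP, L1-tip/PP and U4 transverse.

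The cost is re-analysis of data already held: eight Group II rows, 25 Group I P values and the matching sentences. Whether the U1-tip/S Ver result survives will be known only after the patient-level test.
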